Setting and population: Participants with chronic knee osteoarthritis were recruited through a digital campaign and treated at the Department of Physical Medicine and Rehabilitation of the Antiguo Hospital Civil de Guadalajara "Fray Antonio Alcalde" during the third quarter of 2024 (July–September).

Inclusion criteria: Male and female patients aged 50–80 years. Clinical diagnosis of KOA according to the American College of Rheumatology criteria. Minimum of six months of knee pain. Anteroposterior and lateral knee radiographs (within the past year).

Exclusion criteria: Previous knee surgery. Inflammatory arthropathy. Active infection. Fibromyalgia. Cancer. Severe vascular insufficiency.

Elimination criteria: Absence from one or more RPWT sessions. Voluntary withdrawal at any time for any reason.

Sampling and randomization: Patients were randomly assigned to one of three groups using a sealed opaque envelope method (also known as "paper-draw bag method"). Each envelope contained the designation of one of the three groups ("Experimental Group 1", "Experimental Group 2", or "Control Group"). This simple randomization ensured equal allocation probability and minimized selection bias.

Outcome measures: Sociodemographic data were collected using a standardized internal questionnaire. Pain intensity was assessed using the Numerical Pain Rating Scale (NPRS) at baseline, after the third treatment session, and three months post-baseline. NPRS consists of a 10 cm horizontal line where 0 represents "no pain" and 10 represents "worst imaginable pain." Functionality was measured using the Western Ontario and McMaster Universities Osteoarthritis Index (WOMAC), which evaluates pain (5 items), stiffness (2 items), and physical function (17 items), each scored on a 5-point Likert scale (0 = none, 4 = extreme). Higher scores indicate greater impairment. WOMAC was applied at baseline, after the third session, and three months post-treatment. Radiographic severity of KOA was assessed once using the Kellgren-Lawrence (KL) classification based on weight-bearing anteroposterior knee radiographs. The scale ranges from 0 to 4: 0 = normal; 1 = doubtful; 2 = mild; 3 = moderate; 4 = severe. Outcome evaluations will be conducted at baseline, immediately after the third RPWT session, at the two-month follow-up, and at the four-month follow-up after the first session.

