Sample size calculation: The primary outcome for sample size determination was pain intensity (NPRS). Using a two-tailed α of 0.05, 80% power ($\beta = 0.20$), an expected clinically relevant effect size of 2.0, and a standard deviation of 2.1 (based on prior literature), the required sample size per group was 17 participants. Anticipating a 20% attrition rate, we adjusted the sample to 23 participants per group to preserve statistical power. Therefore, a total of 69 participants were recruited and equally distributed across the three study arms.

Intervention Groups:

- Control group: Patients received 3 weekly RPWT sessions in the supine position with the knee flexed 30°–60°. A total of 2000 shocks per session were applied at the two most painful palpated sites (based on physical examination), using a fixed frequency of 10 Hz and an intensity of 2.0 bar. At the final session, participants were trained to continue with a four-week home-based physical therapy program including superficial thermotherapy, stretching, strengthening, proprioceptive retraining, and general recommendations.
- Experimental group 1: Patients received 3 weekly RPWT sessions in the same position. A total of 2000 shocks were applied to the medial joint line using a non-fixed frequency (10 Hz) and intensity of 2.0 bar. At the final session, they were instructed to follow the same four-week home rehabilitation program as described for the control group.
- Experimental group 2: Patients received 3 weekly RPWT sessions with 2000 total shocks distributed equally over the medial (1000 shocks) and lateral (1000 shocks) joint lines. Frequency was non-fixed (10 Hz), and intensity was 2.0 bar. The same four-week home-based therapy program was prescribed after the third session.

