Blinding: This study will employ a double-blind design. Both participants and the clinical evaluator responsible for conducting the physical and radiographic assessments will be blinded to the group assignments. Participants will be informed that they would receive one of three potential treatment techniques but will not be made aware of the specific approach applied to them. RPWT will be administered by a final-year resident physician in Physical Medicine and Rehabilitation who will be aware of the group allocations but will not be involved in outcome assessments. All data collection and statistical analyses will be conducted by researchers blinded to the group assignments. Furthermore, all treatment sessions will be standardized, with identical instructions, equipment setup, and clinical environments applied across the three groups to minimize performance and detection bias.

Statistical analysis plan

Software: All statistical analyses will be performed using IBM SPSS Statistics version 22.0 (IBM Corp., Armonk, NY, USA).

Descriptive statistics: Descriptive statistics will be computed for all variables. Categorical variables will be reported as frequencies and percentages, while continuous variables will be reported as means and standard deviations or medians and interquartile ranges, depending on their distribution.

Normality testing: The distribution of continuous variables will be assessed using the Kolmogorov–Smirnov test.

Primary outcome: Pain intensity, assessed using the Numerical Pain Rating Scale (NPRS), is defined as the primary outcome.

Secondary outcome: Self-reported physical function, measured with the Western Ontario and McMaster Universities Osteoarthritis Index (WOMAC), is defined as the secondary outcome.

Within-group analysis: To evaluate changes over time within each treatment group (baseline, 2-month, and 4-month assessments), the following tests will be used:

- Paired-samples t-tests for normally distributed data.
- Wilcoxon signed-rank tests for non-normal distributions.
- Bonferroni correction will be applied to adjust for multiple comparisons, when appropriate.

Between-group analysis and interaction Effects: A two-way mixed-design repeated-measures ANOVA will be used to assess:

- The main effect of time.
- The main effect of the group (three levels: pain-site guided therapy, standardized medial line application, and standardized medial + lateral lines application).
- The interaction effect of time × group.

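### The between-technique analysis never adjusts for baseline NPRS or WOMAC: the interaction acts as a change-score test, the group main effect averages baseline in, and neither uses it efficiently

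*Combined protocol and SAP*

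**What the plan says.** The SAP paragraph on between-group analysis and interaction effects gives one model: "A two-way mixed-design repeated-measures ANOVA will be used to assess" a time effect, a group effect with three levels, and their interaction. Post hoc tests are Bonferroni for within-subject effects and Tukey HSD between groups, plus homogeneous subsets. No covariate, ANCOVA or other baseline adjustment appears anywhere in the SAP, for NPRS or for WOMAC. The SAP does not say which effect decides whether the techniques differ.

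The ANOVA text does not list its time levels. The only list in the SAP is in the within-group paragraph: "baseline, 2-month, and 4-month assessments". That baseline is a level of time in the ANOVA is therefore an inference, though the natural one.

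Allocation is unrestricted. The section on sampling and randomization says "This simple randomization ensured equal allocation probability and minimized selection bias", and no stratification by baseline pain or function is described. The sample size section uses "an expected clinically relevant effect size of 2.0, and a standard deviation of 2.1 (based on prior literature") and plans 23 per group.

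**The concern.** Treating the pre-treatment score as one more outcome level leaves two between-group tests, and each handles baseline poorly.

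- **Time × group** compares changes from baseline between arms. A change score subtracts the whole baseline value, although the follow-up score is only partly predicted by it.
- **Group main effect and Tukey HSD** normally compare arm means over all levels of time. One of those levels precedes treatment and cannot show a treatment effect.

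All three arms receive active radial pressure wave therapy and the same home programme, so differences between techniques may be modest and precision matters. Arms are small and allocation is simple, so chance differences in baseline pain are likely. An arm that starts with more pain will tend to look better on the interaction and worse on the main effect. With no deciding test named, the two could point in different directions.

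**Working it through.** **The plan's own figure.** Inputs from the sample size section are "Using a two-tailed α of 0.05, 80% power", difference 2.0 and SD 2.1.
n per arm = 2 × (1.960 + 0.842)² × 2.1² / 2.0² = 17.3, which rounds up to 18; the plan states 17. Allowing 20% attrition, 18/0.8 = 22.5, giving the planned 23. Analysed per arm: 23 × 0.8 = 18.4, taken as 18.

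**Assumptions not in the documents.** 2.1 is the SD of a score; SDs are equal at all visits; the baseline to follow-up correlation r is 0.3, 0.5 or 0.7; the correlation between the 2- and 4-month scores is 0.6; one arm differs from the other two by 2.0 points at both follow-ups.

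**Interaction route, one follow-up visit.**
Variance of change = 2.1² × 2(1 − r). Baseline-adjusted variance = 2.1² × (1 − r²). Ratio of adjusted to change = (1 + r)/2.

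| r | SD of change | adjusted SD | variance ratio |
|---|---|---|---|
| 0.3 | 2.48 | 2.00 | 0.65 |
| 0.5 | 2.10 | 1.82 | 0.75 |
| 0.7 | 1.63 | 1.50 | 0.85 |

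**Main-effect route.** Averaging over baseline, 2 and 4 months turns the difference into (0 + 2.0 + 2.0)/3 = 1.33. The variance of the three-level mean is 2.1² × (3 + 4r + 2 × 0.6)/9, so the SD is 1.63/1.74/1.85 at r = 0.3/0.5/0.7. The effect shrinks by a third, and the noise grows with r.

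**Power of the three-arm omnibus tests, 18 per arm, by simulation** (repeat runs differ by a point or two; the interaction at r = 0.5 ranged from 86% to 88%):

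| Test | r = 0.3 | r = 0.5 | r = 0.7 |
|---|---|---|---|
| Time × group (planned) | 74% | 88% | 98% |
| Group main effect (planned) | 70% | 63% | 56% |
| 4-month score, baseline-adjusted | 84% | 91% | 99% |
| Mean of 2 and 4 months, baseline-adjusted | 93% | 98% | >99% |

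Part of the last row's gain comes from averaging visits. At r = 0.5 an unadjusted change score on the mean of both visits already reaches 90%.

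**Chance baseline gaps.** The standard error of a gap between two arm means is 2.1 × √(2/18) = 0.70 points, or 2.1 × √(2/23) = 0.62 with all 23. The largest of the three gaps is 1 point or more in about 33% of cases at 18 per arm and 24% at 23. If one arm starts 1 point higher, then at r = 0.3/0.5/0.7:

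- the change-score difference moves by −(1 − r) = −0.70/−0.50/−0.30;
- the three-level mean difference moves by +(1 + 2r)/3 = +0.53/+0.67/+0.80;
- under the stated model the baseline-adjusted difference does not move on average.

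**These are one loss, not two.** 2(1 − r) = (1 − r²) + (1 − r)². The extra variance of the change score is exactly the variance contributed by chance baseline gaps.

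**Type I error.** With no true difference (equal correlations of 0.5), the planned tests and the adjusted test each reject in about 5% of simulated trials.

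**The case against.** The mixed ANOVA is conventional and valid, and randomization makes baseline gaps zero on average. That stands: the point is about efficiency, and about error given the gap actually observed.

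The size is uncertain. The documents do not give r, and at r = 0.7 the adjusted 4-month score gains only about a point over the interaction. Equal SDs also matter. If the follow-up SD were 1.3 times the baseline SD, the adjusted-to-change variance ratio would be 0.81/0.91/0.99 rather than 0.65/0.75/0.85. The sample size section does not say whether 2.1 refers to a score or a change. If it is a change SD, the covariate still helps: 17.3 × (1 + r)/2 rounds up to 12/13/15 per arm, against 18.

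The time levels are inferred. The outcome measures section also lists an assessment right after the third session. Were it a fourth level with the same 2.0-point difference, the main effect would be diluted to 2.0 × 3/4 = 1.50 rather than 1.33. The problem would remain, in milder form.

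A reader might infer that the whole technique comparison is a change-score test. The plan does not support this, because it also tests the group main effect and assigns Tukey HSD to the between-group comparisons. A reader might also take a single-visit, Tukey-adjusted change-score comparison as the measure of loss: 67% power against 81% adjusted at r = 0.5. The plan names no such test. Much of that shortfall is multiplicity: at r = 0.5 the change SD equals the planning SD of 2.1, and the same comparison without the Tukey adjustment has about 80% power.

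**Conclusion.** The point holds as a recommendation to improve efficiency. Baseline NPRS and WOMAC are collected, yet neither planned between-group test uses them well. Against the interaction, adjusting the 4-month score adds about 10 percentage points of power at r = 0.3, 3 at r = 0.5 and 1 at r = 0.7. Against the group main effect it adds about 14, 28 and 43 points. The first comparison is modest and the second is large; which one applies depends on a choice the SAP leaves open.

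That baseline is left out as a covariate is plain from the text. The figures rest on the assumed r, follow-up correlation, equal SDs, reading 2.1 as a score SD, 18 analysed per arm, and baseline being a level of time. It would be wrong to conclude that the plan inflates false positives, or to add the precision loss and the baseline-gap effect together as separate harms.

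**What to change.** Replace the primary between-group paragraph as follows.

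- Response: follow-up NPRS, either at one visit named as primary or at 2 and 4 months jointly in a mixed model.
- Terms: technique as factor and baseline NPRS as covariate. In the joint model add visit, technique × visit and baseline × visit.
- Remove baseline from the levels of time.
- Apply the multiplicity-adjusted pairwise comparisons to the baseline-adjusted technique means.
- Do the same for WOMAC, with baseline WOMAC as covariate.
- Keep the mixed ANOVA as a sensitivity analysis.

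The cost is SAP wording and one error degree of freedom (51 to 50 with 54 patients analysed at a single visit). No extra patients, visits or data are needed, and the named software can fit the model. The change should be dated and made before outcomes are compared by arm; if that has already happened, report the adjusted analysis as post hoc.

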RPWT is a non-invasive therapeutic procedure that delivers a single acoustic pulse lasting 1 microsecond to targeted body areas, producing analgesia and promoting healing through a mechanism called mechanotransduction. This mechanotransduction travels through tissues and exerts analgesic, osteogenic, neovascular, and reparative effects. It has been proposed as the main mechanism by which RPWT induces angiogenesis and tissue regeneration at cellular and molecular levels.

Its benefits include analgesia, enhanced protein synthesis, increased vascularization, improved cell proliferation, calcification breakdown, and a protective effect on cartilage and bone.

In OA, RPWT promotes beneficial changes in cartilage and subchondral bone, stimulates chondrocyte activity, and reduces cartilage fissuring. It has anti-inflammatory effects and promotes angiogenesis, helping to relieve pain and improve motor function. RPWT also stimulates meniscal cell proliferation and extracellular matrix repair while modulating central and peripheral sensitization to reduce hypersensitivity and chronic OA-related pain.

RPWT dosing consists of several components that may influence treatment outcomes, including: Frequency (impulses per second), which affects depth and energy distribution (lower frequencies are used for deeper areas; higher for superficial). Number of pulses, with more pulses potentially improving effectiveness but also increasing side effect risks or discomfort. Power, referring to energy per pulse; higher power may be more effective for treating calcifications or dense tissues but may also be more painful. Patient positioning, which may influence effectiveness by improving target orientation and optimizing energy transmission.

Study objectives

General objective: To determine the effectiveness of radial pressure wave therapy (RPWT) using different application techniques in patients with chronic knee osteoarthritis (KOA).

Specific Objectives: 1. To evaluate whether the site of application of RPWT influences clinical outcomes in terms of pain and physical function. 2. To analyze the relationship between the radiographic severity of KOA and clinical outcomes after RPWT. 3. To determine the influence of body mass index (BMI) on clinical outcomes in patients with KOA treated with RPWT.

Materials and methods

Study design: This was a single-blind, randomized controlled trial.

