When the assumption of sphericity is violated, the Huynh–Feldt correction will be applied. Post hoc analyses will include:

- Bonferroni-adjusted pairwise comparisons for within-subject effects.
- Tukey's Honestly Significant Difference (HSD) test for between-group comparisons.

- Homogeneous subset analyses to identify clusters of similar treatment response profiles.

Effect size and power: Partial eta squared (η^2) will be reported to estimate the effect size. Observed power ($1-\beta$) will be documented where appropriate.

Statistical significance: A two-tailed p-value of ≤ 0.05 will be considered statistically significant for all analyses.

References

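### The only pairwise between-arm test is diluted if baseline is one of the ANOVA's time levels, and baseline pain is never used as a covariate

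*Combined protocol and SAP*

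**What the plan says.** The Statistical analysis plan, under between-group analysis and interaction effects, specifies a two-way mixed-design repeated-measures ANOVA. It tests time, group and time x group. The group term is "The main effect of the group (three levels: pain-site guided therapy, standardized medial line application, and standardized medial + lateral lines application". The post hoc list adds a "Honestly Significant Difference (HSD) test for between-group comparisons" and a homogeneous-subset analysis. No covariate, change score, primary time point or primary effect is named for the between-arm comparison.

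The SAP does not list the ANOVA's time levels. Its only list of visits is in the within-group paragraph: "To evaluate changes over time within each treatment group (baseline, 2-month, and 4-month assessments". The Outcome measures section ends with a schedule of four assessments, which adds one right after the third session.

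The Sample size calculation rests on a plain two-arm difference in NPRS: "Using a two-tailed α of 0.05, 80% power", with "an expected clinically relevant effect size of 2.0, and a standard deviation of 2.1 (based on prior literature".

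**The concern.** In a mixed ANOVA the group factor compares each participant's mean over all time levels, and Tukey's test on that factor compares the same means. If baseline is one of the levels, a visit at which randomisation makes the expected difference zero is averaged with visits at which treatment can act. The estimated difference shrinks, and any chance imbalance at baseline is carried into the comparison.

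This matters because Tukey's test is the only stated way to say which application technique differs from which, and that is what Specific Objective 1 asks. A significant interaction beside null Tukey results would leave the trial with no planned pairwise answer. It could also invite the conclusion that the techniques are equivalent. Separately, baseline NPRS is measured on everyone, yet it is not used to sharpen the comparison.

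**Working it through.** **Inputs from the documents.** Difference 2.0, SD 2.1, two-sided alpha 0.05, power 80%, three equal arms, 20% attrition (Sample size calculation).

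**Assumed.** Equal correlation rho between any two visits, taken as 0.3, 0.5 and 0.7, because the documents give none. One arm is better by 2.0 at every follow-up and the other two are equal. There is no expected baseline difference.

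**The plan's own figure.** n = 2 x (1.960 + 0.842)^2 x (2.1/2.0)^2 = 17.31. The plan states "the required sample size per group was 17 participants"; rounded up it is 18. Then 18/0.8 = 22.5, so 23, which matches the planned 23 per arm (17/0.8 = 21.25 would give 22). Since 23 x 0.8 = 18.4, I use 18 completers per arm.

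**Dilution.** With k equally weighted levels including baseline, the group-factor difference is 2.0 x (k-1)/k.
- Three levels: (0 + 2.0 + 2.0)/3 = 1.33.
- Four levels: (0 + 2.0 + 2.0 + 2.0)/4 = 1.50.

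**SD of the quantity compared.**
- Mean over k levels: 2.1 x sqrt((1 + (k-1) rho)/k).
- Mean of two follow-ups: 2.1 x sqrt((1 + rho)/2).
- The same with baseline as covariate: 2.1 x sqrt((1 + rho)/2 - rho^2).
- Month 4 with baseline as covariate: 2.1 x sqrt(1 - rho^2).

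**Tukey power for the differing pair.** The critical value is the studentized-range point for 3 arms and 51 df divided by sqrt(2), which is 2.414. (With one covariate there are 50 df, and it is 2.415.) Noncentrality is difference/(SD x sqrt(2/18)), and power comes from the noncentral t. Example with three levels and rho 0.5: 1.333/(1.715 x 0.3333) = 2.33, giving 47%.

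| Quantity compared | Difference | SD at rho 0.3/0.5/0.7 | Tukey power |
|---|---|---|---|
| Group factor, 3 levels with baseline | 1.33 | 1.53/1.71/1.88 | 58/47/40% |
| Group factor, 4 levels with baseline | 1.50 | 1.45/1.66/1.85 | 75/62/51% |
| Mean of two follow-ups, no covariate | 2.0 | 1.69/1.82/1.94 | 87/81/75% |
| Mean of two follow-ups, baseline covariate | 2.0 | 1.57/1.48/1.26 | 92/94/99% |
| Month 4, baseline covariate | 2.0 | 2.00/1.82/1.50 | 72/81/94% |

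**Interaction, three levels.** The arm deviations (2/3, -1/3, -1/3) have squared sum 2/3. The time deviations of (0, 2, 2) have squared sum 8/3. Their product is 16/9. Noncentrality is 18 x (16/9)/(2.1^2 x (1 - rho)) = 10.4/14.5/24.2. On 4 and 102 df, power is 71/86/98%.

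**The case against.** The strongest reply is that the planned ANOVA already contains an undiluted between-arm test. The time x group interaction measures differential change, and under the assumed effect its power is close to or above that of a month-4 ANCOVA with Tukey adjustment. This stands: the plan would usually detect that something differs. It does not supply the missing step, because the interaction is an omnibus test that is not named primary and no between-arm contrast follows from it.

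A reader might infer that the plan definitely shrinks 2.0 to 1.33. The documents do not support that certainty. The ANOVA's levels are not listed, and the four-visit schedule would give 1.50. The SAP also does not say whether Tukey is run on time-averaged means or at each visit. Pairing it with homogeneous subsets makes the averaged reading likely, but visit-wise testing is not excluded and would not be diluted.

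A reader might also infer that baseline adjustment at month 4 always gains power. With four levels and rho 0.3 it does not: 72% against 75%. Nor is 67%, the power of an unadjusted Tukey test at month 4 alone, the right figure when baseline is left out of the time factor. Tukey on the group factor would then act on the mean of the two follow-ups, with 87/81/75%.

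Finally, Specific Objectives 2 and 3 (the latter "To determine the influence of body mass index (BMI) on clinical outcomes in patients with KOA treated with RPWT") have no stated analysis, and group and interaction are both read at 0.05. These are separate points and lend no support to the dilution argument.

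**Conclusion.** The concern holds conditionally. If baseline is a time level and Tukey acts on the group factor, the only pairwise between-arm test targets 1.33 or 1.50 points instead of the 2.0 for which the trial was sized. Its power at 18 per arm is 58/47/40% or 75/62/51%. If baseline is not a level, there is no dilution; what is lost is the gain from baseline adjustment, 87/81/75% against 92/94/99% on the mean of the two follow-ups. Under either reading no baseline covariate is planned and no primary contrast is named.

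It would go too far to say that the trial as a whole is badly underpowered or its ANOVA invalid, because the interaction is a sound and well-powered randomised comparison. The power figures rest on the assumed correlations, on equal correlation between visits and on a constant 2.0-point effect. The dilution itself does not depend on the correlation.

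**What to change.** Analyse follow-up NPRS with baseline NPRS as a covariate and not as a time level. Use either ANCOVA or a mixed model with visit x arm over the follow-up visits, and list those visits. Name one primary contrast in advance: month 4, or the mean of the follow-ups. The mean is stronger if the benefit is constant, and month 4 suits a benefit expected to build. Report Tukey-adjusted pairwise differences in NPRS points with 95% confidence intervals. State that a group main effect that includes baseline, and its Tukey test, will not be used as evidence of efficacy. Treat WOMAC in the same way.

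The cost is SAP wording only. Baseline NPRS and WOMAC are already collected, and no new data or participants are needed.

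### The only pairwise comparison of techniques, Tukey HSD after a mixed ANOVA, reads as averaging in baseline, which shrinks a 2.0-point follow-up difference in NPRS to 1.33 or 1.50 points

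*Combined protocol and SAP*

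**What the plan says.** In the statistical analysis plan, the paragraph on between-group analysis gives one model, a two-way mixed repeated-measures ANOVA. It tests time, time × group and group, the last described as "The main effect of the group (three levels: pain-site guided therapy, standardized medial line application" plus the medial and lateral technique.

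The post hoc list under that model has three items: Bonferroni pairwise comparisons for within-subject effects, "Tukey's Honestly Significant Difference (HSD) test for between-group comparisons", and homogeneous subsets. It does not say that Tukey is run at a particular visit, on change scores, or with baseline as a covariate. No primary visit is named, and nothing says how a significant interaction is to be followed up between arms.

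The only visits the SAP lists are in the within-group paragraph: "To evaluate changes over time within each treatment group (baseline, 2-month, and 4-month assessments". The ANOVA paragraph lists none. The Outcome measures section ends with a four-visit schedule: baseline, straight after the third session, 2 months and 4 months.

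The sample size section plans for "an expected clinically relevant effect size of 2.0, and a standard deviation of 2.1" on NPRS, the primary outcome.

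**The concern.** In a mixed ANOVA, a post hoc test on the between-subjects factor compares each arm's mean over all levels of time. Baseline precedes treatment, so randomised arms have no technique effect there. Including it pulls every between-technique difference toward zero, and the reported figure no longer estimates the 2.0-point quantity on which the trial was sized.

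The first specific objective asks whether the site of application matters, which is a pairwise question about follow-up. The interaction test is an omnibus test over three arms. If it is significant, the plan's one named tool for saying which technique differs, and by how much, is the diluted one. Homogeneous subsets taken from the same averaged means could put all three techniques into one cluster despite a significant interaction.

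**Working it through.** **The plan's own figure.** Inputs from the sample size section: "Using a two-tailed α of 0.05, 80% power", difference 2.0, SD 2.1. For two means, n = 2 × [2.1 × (1.96 + 0.84) / 2.0]² = 17.3, which rounds up to 18 per arm; the plan states that "the required sample size per group was 17 participants". With 20% attrition, 18 / 0.8 = 22.5, so 23, as planned. I use 18 per arm (after attrition) and 23 per arm (no attrition).

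**Assumptions.** One arm is 2.0 points better than both others at every post-baseline visit. The arms are equal at baseline, SD is 2.1 at each visit, and every pair of visits has the same correlation rho. The documents give no rho, so 0.3, 0.5 and 0.7 are shown.

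**Dilution.** With V visits, one of them baseline, the expected difference in averaged scores is 2.0 × (V − 1)/V.
- Three visits: 2.0 × 2/3 = 1.33.
- Four visits, effect at all three post-baseline visits: 2.0 × 3/4 = 1.50.
- Four visits, effect only at 2 and 4 months: 2.0 × 2/4 = 1.00.

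None of these depends on rho, SD or sample size.

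**Power for one truly different pair.** The test uses the noncentral t with df = 3(n − 1), noncentrality d / [SD × √(2/n)], and the studentized-range critical value divided by √2 (2.414 at n = 18).
- SD of the three-visit mean: 2.1 × √[(1 + 2rho)/3].
- SD of the mean of the 2- and 4-month visits: 2.1 × √[(1 + rho)/2].
- Residual SD at 4 months adjusted for baseline: 2.1 × √(1 − rho²).

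Example at rho 0.5, n = 18: the three-visit SD is 2.1 × √(2/3) = 1.71, its standard error is 1.71 × √(2/18) = 0.57, the noncentrality is 1.33/0.57 = 2.33, and power is 47%.

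| Comparison | Expected difference | Power at n = 18, rho 0.3/0.5/0.7 | Power at n = 23, rho 0.3/0.5/0.7 |
|---|---|---|---|
| Tukey on group factor, 3 visits | 1.33 | 58/47/40% | 71/60/51% |
| Tukey on group factor, 4 visits, effect at all 3 post-baseline | 1.50 | 75/62/51% | 87/75/64% |
| Mean of 2 and 4 months, Tukey | 2.0 | 87/81/75% | 94/91/86% |
| 4 months, baseline-adjusted, Tukey-type | 2.0 | 72/81/94% | 84/91/98% |
| 4 months alone, unadjusted, Tukey | 2.0 | 67% | 80% |

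If four visits enter and the effect is present only at 2 and 4 months, power is 28% at rho 0.5 and n = 18.

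**Interaction test.** In simulated three-visit trials under the same assumptions at n = 18, time × group is significant in about 72/87/98%. At rho 0.5, Tukey separates a given truly different pair in only about 47% of the trials with a significant interaction, and separates no pair in about 36% of them.

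**The case against.** The strongest reply is that the SAP never says Tukey is run on time-averaged means. It says only that the test is for comparisons between groups, and the list is introduced as what the post hoc analyses will include, so it need not be exhaustive. Time × group is itself tested in the within-subject part of the model, so the Bonferroni item might be meant to cover its follow-up. This stands in part: the averaged reading is an inference. But it is the ordinary meaning of a Tukey post hoc under this model, and no other line clearly supplies a follow-up contrast between arms.

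A reader might infer that a real 2.0-point difference would usually be missed. The documents do not support that. Three-visit pairwise power is below 50% only at about 17 to 18 per arm with rho of roughly 0.45 or more, or at higher rho with 23 per arm, and rho is undocumented. In the scenario used, two pairs truly differ, and at least one of them separates in about 74/63/55% of trials at n = 18 and 85/76/67% at n = 23. A significant interaction with no Tukey pair separated occurs in about 18 to 45% of trials at n = 18 and 13 to 33% at n = 23, a minority throughout. Nothing in the plan says a null Tukey result overrides a significant interaction, so it does not follow that the arms would be reported as not different.

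Nor is the shrinkage one known factor. The three visits come from the within-group paragraph, and the outcome schedule has four.

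Some of the shortfall against 80% also comes from the three-way Tukey adjustment: an undiluted, unadjusted 4-month comparison at n = 18 has only 67%.

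**Conclusion.** The point holds in limited form. Read naturally, the one named pairwise procedure gives a diluted estimate: 1.33 points for a true 2.0 with three visits, or 1.50 with four when the effect is present at all three post-baseline visits. That much is arithmetic, given the averaged reading and a constant follow-up effect. The power loss also rests on SD 2.1 and an assumed rho. With three visits, pairwise power is 47% at 18 per arm and 60% at 23 for rho 0.5, against 81% and 91% on the mean of the two follow-ups.

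The trial as a whole would not necessarily miss the effect, because the interaction test is sensitive to it. What the plan lacks is an undiluted statement of which technique differs and by how much, and that is the trial's main question. This is more than missing detail, since following the text as it stands produces the wrong estimate.

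**What to change.** Replace the Tukey and homogeneous-subset items with:

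> Pairwise technique differences in NPRS (and WOMAC) will be estimated at the 4-month visit, adjusted for the baseline score (ANCOVA), with a Tukey-type adjustment for the three comparisons. The 2-month visit will be analysed in the same way as supportive. No Tukey or homogeneous-subset output will be taken from the group factor averaged over time including baseline.

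The documents name no primary visit, so the sponsor must confirm 4 months as that visit and state which visits enter the ANOVA.

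Adjusting for baseline is better than simply leaving it out: at rho 0.5 and 18 per arm, 4-month power rises from 67% to 81%. At rho 0.3 it reaches only 72%, so the gain depends on the correlation actually seen. The mean of the 2- and 4-month visits, also adjusted for baseline, would have more power (94% at rho 0.5 and 18 per arm), but it answers a question about average follow-up pain, not pain at 4 months.

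The cost is a small change to the model specification and the SPSS request, with no new data or patients.
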